3.2.2 Secondary Study Endpoints

The secondary endpoints will consist of questionnaires measuring the patients function. We will utilize the ASES Shoulder and QuickDASH scores. Based on their responses and their scores at the time prior to and after their barbotage therapy begins, we can determine a primary endpoint with a 10% change between baseline and their final visit.

4 Study Enrollment and Withdrawal

Eligible patients include patients at least 18 years of age, ASA class I-II, and patients diagnosed with calcific tendonitis.

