2.1 Primary Objective

The primary objective of the study is to determine the efficacy of barbotage without cortisone on patients with calcific tendonitis by measuring their clinical improvement via VAS, QuickDASH, and ASES Shoulder scores and radiographic size of calcium deposit.

3 Study Design and Endpoints

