3.2 Study Endpoints

3.2.1 Primary Study Endpoints

The primary study endpoint will focus on the decrease in pain of the affected shoulder measured by VAS scores. Based on their responses and their scores at the time prior to and after their barbotage therapy begins, we can determine a primary endpoint with a 10% change between baseline and their final visit. We would also like to observe the affected rotator cuff tendon and measure the efficacy of barbotage therapy via shoulder radiograph. Shoulder X-Ray is considered standard of care and we expect a resolution in size of the calcified deposit by at least 10% after aspiration and lavage.

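### The plan does not fix which outcome carries the primary claim: 3.2.2 calls ASES and QuickDASH both secondary and primary, on an undirected 10% change

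*Combined protocol and SAP*

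**What the plan says.** Four places in the protocol bear on which outcome is primary.

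- **3.2.1 Primary Study Endpoints** names pain: "The primary study endpoint will focus on the decrease in pain of the affected shoulder measured by VAS scores". Under the same heading it adds radiographic deposit size with its own threshold: "we expect a resolution in size of the calcified deposit by at least 10% after aspiration and lavage".
- **3.2.2 Secondary Study Endpoints** opens with "The secondary endpoints will consist of questionnaires measuring the patients function" and names ASES and QuickDASH. Its last sentence then says of those scores: "Based on their responses and their scores at the time prior to and after their barbotage therapy begins, we can determine a primary endpoint", and continues "with a 10% change between baseline and their final visit". The whole sentence also appears in 3.2.1, where it refers to VAS.
- **2.1 Primary Objective** judges efficacy by "measuring their clinical improvement via VAS, QuickDASH, and ASES Shoulder scores and radiographic size of calcium deposit", with no ranking among the four measures.
- **8.1 Sample Size** gives one alpha of 0.05, power 0.80 and d = 0.6, and names no outcome. It sets one generic rule for continuous variables and one for binary variables, with no order of testing and no split of alpha.

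The statistical line of the Protocol Summary mentions ANOVA or t tests and a correlation between scores. It names no primary outcome either.

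**The concern.** Within one short section the function scores are both secondary and primary, and the primary objective includes them too. When results arrive, a report could lead with VAS, ASES, QuickDASH or deposit size and cite the protocol in support of each. A single 0.05 with no named outcome does not limit the chance of a false primary claim if that choice is open.

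The criterion for function adds a second difficulty. It is met "with a 10% change between baseline and their final visit", which states neither a direction nor a comparison between arms. Taken literally, a worsening of 10% satisfies it as well as an improvement of 10%. A change from baseline within patients also does not answer the randomised question, which the Protocol Summary frames as a comparison of barbotage alone with barbotage plus cortisone.

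**Working it through.** **1. Status of each outcome, side by side**

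| Outcome | 2.1 | 3.2.1 | 3.2.2 | 8.1 |
|---|---|---|---|---|
| VAS pain | under primary objective | primary | – | not named |
| Deposit size | under primary objective | under primary heading | – | not named |
| ASES | under primary objective | – | secondary (heading and first sentence), primary (last sentence) | not named |
| QuickDASH | under primary objective | – | secondary (heading and first sentence), primary (last sentence) | not named |

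If the last sentence of 3.2.2 is struck out as a paste from 3.2.1, that section becomes consistent. Section 2.1 still lists all four outcomes together, and 3.2.1 still has two outcomes under the primary heading.

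**2. Does the sample size show which outcome is primary?**

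Inputs from 8.1: d = 0.6, alpha 0.05, power 0.80. Sidedness is not stated; two-sided is assumed. The normal approximation per arm is

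n = 2(z₀.₉₇₅ + z₀.₈₀)² / d² = 2(1.960 + 0.842)² / 0.36 = 43.6, so 44 per arm and 88 in total.

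The exact two-sample t-test needs 45 per arm, 90 in total. The stated figure of more than 128 is not reproduced. An effect of d = 0.5 gives 64 per arm, 128 in total. The mismatch is a separate matter. Here it means only that the calculation does not identify the outcome it was made for.

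**3. Direction and contrast of the 10% criterion**

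- 3.2.1 gives a direction for pain (decrease) and for the deposit (resolution).
- 3.2.2 gives none. It also does not say whether the 10% applies per patient, to an arm mean or between arms.
- 2.1 speaks of clinical improvement, which implies a direction, but does not connect it to the 10%.

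**4. Error rate if the choice of outcome is left open**

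Assumptions: k outcomes, each tested two-sided at 0.05, no true difference on any, and a primary claim made if at least one is significant. The plan states no such rule.

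Under independence the rate is 1 − 0.95^k:

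- k = 1 (VAS alone): 0.05
- k = 3 (VAS, ASES, QuickDASH): 1 − 0.857 = 0.143
- k = 4 (adding deposit size): 1 − 0.815 = 0.185

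Scores from the same patients will be correlated, and the documents give no correlations. For normal test statistics with a common correlation ρ, the rate is 1 − P(all |Z| < 1.96):

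| Assumed ρ | Three scores | Four outcomes |
|---|---|---|
| 0 | 0.143 | 0.185 |
| 0.3 | 0.136 | 0.174 |
| 0.5 | 0.125 | 0.156 |
| 0.7 | 0.109 | 0.130 |
| 0.8 | 0.098 | 0.114 |

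Across the table the rate is about 2 times (0.098/0.05) to 3.7 times (0.185/0.05) the stated 0.05.

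**The case against.** The best defence is that the intent is clear enough. The heading and first sentence of 3.2.2 classify the questionnaires as secondary, 3.2.1 uses the singular for its primary endpoint and attaches it to VAS, and the offending sentence is an exact repeat. Section 2.1 states an objective, and listing the measures that inform an objective does not make each one a primary endpoint. It also says improvement, so nobody would count deterioration as success.

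Much of this stands. VAS is probably the intended primary outcome, and the repeated sentence is probably a slip. But 2.1 is worded independently of that sentence and does not rank the measures, and deposit size under the primary heading is not part of the slip. No other section settles the order.

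Four stronger readings are tempting, and the documents do not support them:

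- *The plan intends to claim success on function if VAS fails.* It leaves this open on a literal reading, but no section sets out such a rule.
- *Patients who worsen will be counted as responders.* Section 8.1 provides tests for binary variables, but nowhere are function scores said to be turned into patient counts. Nor do the documents give the scoring direction of either scale, so no worked example of a worsening patient can be drawn from them.
- *The true type I error is 18.5%.* That needs four outcomes, independence and a rule that any one suffices. It also concerns tests for a difference, whereas section 1.2 additionally asks whether barbotage alone does as well, which these rates do not address.
- *The figure of 128 shows that alpha was split over four outcomes.* A t-test with d = 0.6 and alpha 0.05/4 does need 128 in total, but 8.1 states alpha 0.05 and no split, and d = 0.5 at 0.05 gives the same total.

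**Conclusion.** The concern holds as an inconsistency with a practical consequence: the protocol does not fix which outcome carries the primary claim, and the criterion for function is an undirected change from baseline that worsening would also meet and that does not compare the arms. Both conclusions rest on the text alone.

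The size depends on assumptions. With VAS as the only primary outcome, the false-claim rate is 0.05. If any of the three scores could carry the claim, it is 0.143 under independence and 0.136 to 0.098 for correlations of 0.3 to 0.8. With deposit size as a fourth outcome it is 0.185, and 0.174 to 0.114. These figures show what is at risk while the choice stays open; they are not the error rate of a stated procedure. The matter should be settled before any unblinded comparison is seen, because a later choice would look data-driven.

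**What to change.** Change three sections together, since correcting only 3.2.2 and 2.1 would leave deposit size, and the same 10% wording, under the primary heading.

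- **3.2.1:** name one primary endpoint, the between-arm difference in change in VAS pain from baseline to month 6. Move deposit size to the secondary endpoints.
- **3.2.2:** in the last sentence, call ASES and QuickDASH secondary endpoints. Replace the 10% change with the between-arm difference in change from baseline to month 6, and state the direction of improvement for each scale from its scoring manual.
- **2.1:** judge the primary objective on VAS, and place ASES, QuickDASH and deposit size under a secondary objective.

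The alpha of 0.05 in 8.1 then belongs to one test and needs no split. The cost is a few sentences; enrolment, visits and data collection do not change. The downside is that a result on function or deposit size alone can no longer be called primary.

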4.1 Inclusion Criteria

In order to be eligible to participate in this study, an individual must meet all of the following criteria:

- Must be at least 18 years of age and younger than 90 years of age
- Diagnosed with calcific tendonitis and ruled out other shoulder-related pathologies
- Failed 1st line therapy (physical therapy and cortisone injection)
- Intention to receive barbotage with cortisone as standard of care
- 3 or more months of shoulder pain
- Finding of one or more calcifications ≥ 5 mm in size on either sonogram or radiograph, located on the supraspinatus tendon
- Positive Hawkin's test or Neer's sign for impingement

CONFIDENTIAL

This material is the property of the NYU School of Medicine and Langone Medical Center. Do not disclose or use except as authorized in writing by the study sponsor

4.2 Exclusion Criteria

An individual who meets any of the following criteria will be excluded from participation in this study:

- Legally incompetent or mentally impaired (e.g. minors, Alzheimer's subjects, dementia, etc.)
- Osteoarthritis of the glenohumeral joint of the affected shoulder
- Previous surgery or barbotage to the affected shoulder
- History of prior allergic/hypersensitivity reactions related to the study medication
- Shoulder instability, glenohumeral arthritis, AC pathology, inflammatory arthropathy, fibromyalgia, frozen shoulder or cervical radiculopathy
- Sub-acromial injection with a corticosteroid or treatment by ESWT during the last 3 months before inclusion
- Younger than 18 years of age or older than 90
- Any patient considered a vulnerable subject

4.3 Vulnerable Subjects

We do not intend to enroll vulnerable subjects.

4.4 Strategies for Recruitment and Retention

Patients identified by participating orthopaedic surgeons at NYU Langone Orthopedic Hospital with calcific tendonitis who meet inclusion criteria will be eligible for the study. When the patients arrive at the physician office for a standard of care visit, study team members will provide the potential patient subjects with information on the study and ask the patient for their consent to be in the study.

4.4.1 Use of DataCore/Epic Information for Recruitment Purposes

This study will utilize EPIC to identify subjects.

Patients will be identified by participating orthopaedic surgeons at NYU Langone Orthopedic Hospital.

- TP agrees to permit study team to directly contact potential subjects on behalf of TP.
- The patients will be contacted by the study team in person when patients arrive at the physician office for a standard of care visit

Subjects will be asked if they are interested in participating in this specific study. Should the potential subjects agree, the study team will provide the subjects with information regarding the next steps for participation.

If a subject requests information regarding opting out of further recruitment for all research, subjects will be directed to contact [contact] or [name].

4.5 Duration of Study Participation

The study intervention phase of physical study will last for 24 months. The participants will require 3 follow-up visits.

4.6 Total Number of Participants and Sites

Recruitment will end when approximately 140 participants are enrolled. All patients will be enrolled from NYULMC.

CONFIDENTIAL

This material is the property of the NYU School of Medicine and Langone Medical Center. Do not disclose or use except as authorized in writing by the study sponsor

4.7 Participant Withdrawal or Termination

4.7.1 Reasons for Withdrawal or Termination

Participants are free to withdraw from participation in the study at any time upon request. An investigator may terminate participation in the study if:

- Any clinical adverse event (AE), laboratory abnormality, or other medical condition or situation occurs such that continued participation in the study would not be in the best interest of the participant
- The participant meets an exclusion criterion (either newly developed or not previously recognized) that precludes further study participation.

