6.3 Time Period and Frequency for Event Assessment and Follow-Up

The occurrence of an AE or SAE may come to the attention of study personnel during study visits and interviews of a study participant presenting for medical care, or upon review by a study monitor. All AEs including local and systemic reactions not meeting the criteria for SAEs will be captured on the appropriate RF. Information to be collected includes event description, time of onset, clinician's assessment of severity, relationship to study intervention (assessed only by those with the training and authority to make a diagnosis), and time of resolution/stabilization of the event. All AEs occurring while on study must be documented appropriately regardless of relationship. All AEs will be followed to adequate resolution.

Any medical condition that is present at the time that the participant is screened will be considered as baseline and not reported as an AE. However, if the study participant's condition deteriorates at any time during the study, it will be recorded as an AE. UPs will be recorded in the data collection system throughout the study.

Changes in the severity of an AE will be documented to allow an assessment of the duration of the event at each level of severity to be performed. AEs characterized as intermittent require documentation of onset and duration of each episode.

CONFIDENTIAL

This material is the property of the NYU School of Medicine and Langone Medical Center. Do not disclose or use except as authorized in writing by the study sponsor

The PI will record all reportable events with start dates occurring any time after informed consent is obtained until 7 (for non-serious AEs) or 30 days (for SAEs) after the last day of study participation. At each study visit, the investigator will inquire about the occurrence of AE/SAEs since the last visit. Events will be followed for outcome information until resolution or stabilization.

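### Ending participation after the one-time Day 0 procedure (section 4.7.1) can only remove outcome data, and some permitted grounds can themselves be treatment failures

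*Combined protocol and SAP*

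**What the plan says.** Section 4.7.1 opens with "An investigator may terminate participation in the study if" and gives two grounds. The first is an adverse event, laboratory abnormality or other condition, but only where it "occurs such that continued participation in the study would not be in the best interest of the participant". The second is "The participant meets an exclusion criterion (either newly developed or not previously recognized) that precludes further study participation".

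The exclusion criteria in 4.2 include "Previous surgery or barbotage to the affected shoulder" and "Shoulder instability, glenohumeral arthritis, AC pathology, inflammatory arthropathy, fibromyalgia, frozen shoulder or cervical radiculopathy".

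Attachment A marks the study intervention at Visit 1 only. It schedules VAS at all four visits, and ASES, QuickDASH and radiographs at the first and last. Section 3.2.1 bases the primary VAS endpoint on the change from baseline to the final visit, which 5.2.4 places at month 6.

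Under 6.3 the investigator asks about adverse events at each visit and records new ones "until 7 (for non-serious AEs) or 30 days (for SAEs) after the last day of study participation". The same section keeps unresolved events under follow-up and asks that possibly related events arising after termination be notified to the sponsor.

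Section 5.1.1 lists the three follow-up visits and the before-and-after VAS, ASES and QuickDASH as standard of care. Section 5.2.4 labels the month-6 X-ray as research. Section 4.7.2 takes the data of patients who withdraw out of REDCap and replaces those patients. Its heading also covers termination, but its sentence does not.

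**The concern.** In a trial with continuing treatment, a clause like 4.7.1 protects patients by stopping exposure. Here exposure is complete on Day 0. Ending participation afterwards spares the patient only the remaining assessments, and it costs the trial that patient's month-6 value.

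The loss is not necessarily random. A patient who goes on to surgery or a second barbotage, or whose shoulder stiffens, has probably done badly, and that same event can be the ground for termination. If one arm has more such events, it loses more of its poor outcomes, and the month-6 comparison flatters it. New non-serious adverse events in those patients also stop being routinely recorded 7 days after participation ends.

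**Working it through.** **1. What is left to stop after Day 0.** Attachment A shows one administration, at Visit 1. What remains is VAS at 6 weeks and 3 months; VAS, ASES, QuickDASH and X-ray at month 6; and the adverse event enquiry at each visit. Termination before month 6 therefore removes the primary endpoint value and stops no study treatment.

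**2. Which 4.2 criteria can newly arise as harm or failure.**
- Surgery or repeat barbotage of the study shoulder: yes.
- Frozen shoulder: yes.
- Hypersensitivity: weak. The criterion is "History of prior allergic/hypersensitivity reactions related to the study medication", which naturally refers to the time before enrolment.
- Sub-acromial steroid injection or ESWT: no, as worded. It is tied to the 3 months before inclusion.

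**3. Whether the loss could differ by arm.** Section 1.3.1 names temporary pain and possibly prolonged inflammation as risks of not receiving the steroid. A difference between arms in failures is therefore plausible on the protocol's own account, but no rate is given.

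**4. What survives termination.** Section 6.3 preserves follow-up of unresolved events and notification of later related ones. It does not restore scheduled enquiry, VAS, questionnaires or the X-ray. Section 8 defines no analysis population and no method for missing outcomes.

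**5. Size.** The plan has no figure for terminations to reproduce. With 140 patients randomised 1:1 there are 70 per arm, so each lost patient is 1/70 = 1.4% of an arm.

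The following is an illustration only; every input in it is an assumption. A share f of one arm is lost and none of the other. The outcome is normal with SD 1, and the tendency to be lost has correlation r with a worse outcome. The mean of the retained patients shifts towards better by

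shift = r × φ(z) / (1 − f), where z is the (1 − f) normal quantile.

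| f | Patients of 70 | φ(z)/(1 − f) | Shift, r = 0.5 | Shift, r = 1 |
|---|---|---|---|---|
| 5% | 3.5 | 0.109 | 0.05 SD | 0.11 SD |
| 10% | 7 | 0.195 | 0.10 SD | 0.20 SD |
| 15% | 10.5 | 0.274 | 0.14 SD | 0.27 SD |

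A simulation with 70 analysed per arm, 5,000 runs per case and lost patients replaced gave similar shifts. With no true difference, the two-sided type I error was 0.065 at f = 5%, r = 0.5 and 0.41 at f = 15%, r = 1. The last case is extreme, because it loses exactly the worst outcomes. The simulation builds in replacement, so its error rates do not isolate 4.7.1; the shift formula does not need replacement. If both arms lose the same share in the same way, the shift cancels from the difference. A larger sample does not remove it when they do not.

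I do not measure these counts against the allowance in 8.1. It is stated as 10 per group, but 140 − 128 = 12 leaves 6 per group. Also, a patient who could be terminated need not be.

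**The case against.** The clause is milder than it may look. It is discretionary, and each ground carries a qualifier: best interest for adverse events, and preclusion of further participation for exclusion criteria. Three stronger readings are tempting, and the documents do not support them.

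- A reader might infer that follow-up stops for exactly the patients who are harmed or fail. The grounds also cover unrelated conditions and ineligibility found late, and termination is not automatic.
- A reader might infer that every treated patient becomes terminable, having now had barbotage. That ignores the requirement that the criterion preclude further participation.
- A reader might infer that drug reactions are cut short in the cortisone arm only. The hypersensitivity criterion concerns prior reactions, and 6.3 keeps the event that triggered termination under follow-up until it is resolved, the patient is lost, or it is otherwise explained.

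It is also fair to say that leaving the study need not stop routine care, since 5.1.1 treats the visits and scores as standard of care.

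All of this narrows the point without removing it. No section says which criteria preclude follow-up once a one-time procedure is done, so the judgement is made after outcomes have begun to emerge. No section says that routinely collected scores stay in the trial data after termination, and the month-6 X-ray is a research procedure in any case.

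**Conclusion.** The point holds in limited form. After Day 0, termination under 4.7.1 can only remove study outcome data, including the primary endpoint. At least two criteria in 4.2 can arise as treatment failure, so the loss can depend on outcome and differ by arm.

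The size is unknown because the documents give no rate of termination, re-intervention or frozen shoulder. Under the assumptions shown (5% to 15% lost from one arm only, correlation 0.5 to 1), the shift would be about 0.05 to 0.27 SD in favour of the arm that loses patients; with equal loss in both arms it would be near zero. The finding does not depend on 4.7.2, but if deletion and replacement were applied to terminated patients, the loss would also become invisible. The change is worth making because it is cheap, not because a large bias has been shown.

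**What to change.** Reword 4.7.1 to separate omission of a study procedure from the end of outcome follow-up:

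- After Day 0, an adverse event or a newly developed or newly recognised exclusion criterion may lead to omission of an individual study procedure, for example the research X-ray. It does not by itself end outcome follow-up.
- VAS, ASES, QuickDASH and adverse events continue to be collected as scheduled to month 6 and stay in the trial data. The event or re-intervention is recorded with its date.
- Exceptions: the patient withdraws consent, can no longer consent, or the follow-up contact itself is not in the patient's interest. The reason is recorded.

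The cost is a wording amendment and a few more follow-up assessments, at visits already scheduled for every patient.
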